2.2 Relevance of project

Theoretical arguments have been made that surgery for FAI may prevent the development of arthritis^{1,4}, but there is no evidence for this. Surgery might be indicated to relieve current symptoms, but an equally strong argument can be made that a well-constructed regime of conservative care will reduce the symptoms of hip impingement.

Hip arthroscopy is a rapidly expanding area of surgery, and FAI is one of the most frequent indications. The key elements of surgery for FAI that have been developed through open surgery are achievable by hip arthroscopy. Avoiding the more invasive procedure and prolonged periods of nonweight-bearing of open surgery have apparent advantages for patients. But arthroscopic FAI surgery has evolved quickly – more quickly than our understanding of the natural history of the disease⁴⁵⁻⁴⁸, so it is now not clear whether surgery offers real benefit over a package of best conservative care.

In this context, an RCT to compare arthroscopic surgery and post-operative rehabilitation with best conservative care would be appropriate. However, it is a rapidly developing field, currently practiced by relatively few surgeon-innovators and specialists in non-operative care: These groups may not be in

equipoise. This presents special problems in the performance of a trial.³⁴ In addition, patients are likely to have strong views about whether they would prefer surgical or conservative treatment, raising questions about their preparedness to be randomised.

In addition we have referred to our own experience of a study with some similarities - the UK Heel Fracture study, which had a recruitment rate of 30%. Before a full RCT could proceed we believe it would be essential to determine the likely recruitment rate. The proposed feasibility study will explore whether a substantive trial could succeed, and if so, how best it might be designed. It is not designed to measure clinical effect, but to estimate the most important parameters that will be needed to design a substantive trial. It includes a pilot to agree the intervention protocols, test the proposed processes of a substantive trial, and, crucially, to estimate recruitment rate.

3. Study design

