Trial information consultation

Patients will attend a Trial Information Consultation with a trained clinical researcher. Information will again be provided about FAI and its possible treatments, and about this pilot trial. Patients will be given an opportunity to ask questions. Patients will then be invited to give their consent to become participants in the trial. Patients who wish to take more time to consider will be given an opportunity to do so. Patients who agree to take part will complete baseline questionnaires at this consultation.

Treatment allocation

Participants will be randomly allocated to arthroscopic surgery and post-operative rehabilitation or best conservative care using 1:1 secure centralised telephone randomisation provided by Warwick CTU. Patients will usually be informed of their allocation at the Trial Information Consultation, and plans for delivery of the intervention will begin to be made there.

Post randomisation withdrawals

Participants may withdraw from the trial at any time without prejudice. If patients decide to have the treatment to which they were not randomised, participants will be followed-up wherever possible and

data collected as per the protocol until the end of the trial. The primary analysis will be on an intention-to-treat basis with a secondary per-protocol analysis.

Blinding

The patients cannot be blind to their treatment. The treating surgeons will, of course, not be blind to the treatment, but will take no part in outcome assessment for the trial. The functional outcome data will be collected and entered onto the trial central database via postal questionnaire by a research assistant who will be blind to the treatment allocation. The statistical analysis will also be performed blind.

Consent

Written informed consent will be obtained by a researcher delegated and trained by the research team. In general, from initial consultation to the day of surgery or start of best conservative care so there will be sufficient time for the patients to consider taking part in the trial. Any new information that arises during the trial that may affect patients' willingness to take part will be reviewed by the Trial Management Group; if necessary this will be communicated to all participants by the Trial Coordinator. A revised patient information sheet (PIS) will be provided and revised consent form will be completed if necessary.

Sample size

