This pilot is not powered to estimate a treatment effect, rather to achieve a reasonable confidence interval around the estimate of the recruitment rate. Previous studies in orthopaedic surgery of operative vs. non-operative treatments have achieved recruitment rates of around 30%, so we have modelled around this rate.

Table 1 shows 95% confidence intervals around various recruitment rates for a range of scenarios. Sixty patients will allow a 95% CI of 18 to 41% if the true recruitment rate is 30% and we judge this to be a good balance between cost and duration of the pilot study and the required precision of the estimate.

| Rate (%) | n=15 | n=30 | n=60 | n=90 | n=120 |
|----------|--------------|--------------|---------------------|--------------|--------------|
| 10 | (0.0, 25.2) | (0.0, 20.7) | (2.4, 17.6) | (3.8, 16.2) | (4.6, 15.4) |
| 20 | (0.0, 40.2) | (5.7, 34.3) | (9.9, 30.1) | (11.7, 28.3) | (12.8, 27.2) |
| 30 | (6.8, 53.2) | (13.6, 46.4) | (18.4, 41.6) | (20.5, 39.5) | (21.8, 38.2) |
| 40 | (15.2, 64.8) | (22.5, 57.5) | (27.6, 52.4) | (29.9, 50.1) | (31.2, 48.8) |
| 50 | (24.7, 75.3) | (32.1, 67.9) | (37.3, 62.7) | (39.7, 60.3) | (41.1, 58.9) |

Table 1

We propose to approach 60 eligible patients across the four centres in order to estimate a recruitment rate with sufficient precision to plan a full RCT. Last year, the participating surgeons in four collaborating centres performed 221 arthroscopic FAI procedures in which at least 204 would have been eligible for this pilot. We therefore expect to complete an approach to 60 patients in 12 months.

Trial treatments

Arthroscopic hip surgery

As a relatively new procedure, there are a variety of surgical techniques for arthroscopic FAI surgery. We have chosen a group of surgeons who perform similar techniques which are typical of the majority of surgeons around the world, and representative of those used widely in the UK. The surgeons are all suitably trained and experienced. They will agree the final details of the following operative and post-operative rehabilitation protocol during a workshop in the pre-pilot phase of the trial.

The provisional operative protocol is:

- General anaesthetic with muscle relaxation.
- Supine or lateral patient positioning.
- Operating table with facility for traction and allows range of movement testing.
- Arthroscopy of central compartment.

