3.9 End of trial

The pilot study will be complete when we have approached 60 patients to seek consent for randomisation or when it has become apparent that it is not feasible within 18 months. All patients who are randomised will be followed up for 1 year.

4. Data Management

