4.2 Statistical Analysis

The pilot study is not designed or powered to assess the size of any treatment effect, rather to estimate recruitment rate. The recruitment rate will be estimated based on data collected and a 95% confidence interval determined for this estimate. Treatment differences will be estimated for the primary outcome measure (NAHS) and all secondary outcome measures (IHOT-33, SF-36 and EQ-5D) at 3, 6 and 12 months. In addition to treatment differences the variability (standard deviation) of the outcome measures will be estimated in the target population. Together with the estimated treatment differences, the variability and recruitment rate will be used in power analysis to develop a range of potential trial designs, with recommendations as to which the most feasible option.

In addition to power analysis, summary data measures (e.g. means, medians and standard deviations) will be presented for all outcome measures at each occasion and inferences will be made on temporal changes and any potentially interesting effects within subgroups identified for future work. Analysis will be undertaken in SPSS® and R (<http://www.r-project.org/>) as appropriate.

It seems likely that some data may not be available due to voluntary withdrawal of patients, lack of completion of individual data items or general loss to follow-up. Where possible the reasons for data 'missingness' will be ascertained and reported. Although missing data is not expected to be a problem for this study, the nature and pattern of the missing data will be carefully considered — including in particular whether data can be treated as missing completely at random (MCAR). If judged appropriate, missing data will be imputed, using the multiple imputation facilities available in R (<http://www.r-project.org/>). The resulting imputed datasets will be analyzed and reported, together with appropriate sensitivity analyses. Any imputation methods used for scores and other derived variables will be carefully considered and justified. Reasons for ineligibility, non-compliance, withdrawal or other protocol violations will be stated and any patterns summarized. More formal analysis, for example using logistic regression with 'protocol violation' as a response, may also be appropriate and aid interpretation.

5. Trial Oversight

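### Section 4.2 makes the pilot's own treatment difference an input to the full-trial power analysis, although the pilot (about 9 patients per arm at the planned 30% recruitment rate) is declared unable to measure effect

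*Protocol*

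**What the plan says.** The protocol disclaims effect estimation in three places. Section 2.2 says of the feasibility study: "It is not designed to measure clinical effect, but to estimate the most important parameters". The sample size part of section 3.5 says: "This pilot is not powered to estimate a treatment effect". Section 4.2 opens with a similar disclaimer and names the recruitment rate as the target of estimation.

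Section 4.2 then plans to estimate treatment differences at 3, 6 and 12 months for NAHS (primary), IHOT-33, SF-36 and EQ-5D, and to estimate their standard deviations. It continues: "Together with the estimated treatment differences, the variability and recruitment rate will be used in power analysis". The product of that analysis is several candidate full-trial designs, with advice on which is most feasible.

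The size of the pilot is set by the number approached, not the number randomised. Section 3.5: "We propose to approach 60 eligible patients across the four centres". Section 3.9: "The pilot study will be complete when we have approached 60 patients to seek consent for randomisation". Allocation is made "using 1:1 secure centralised telephone randomisation provided by Warwick CTU". The planning recruitment rate is 30%.

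The protocol gives no minimum important difference, or other external target effect, for NAHS or IHOT-33.

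**The concern.** The section uses as a design input the one quantity that the protocol says the pilot cannot supply. Required sample size varies with the inverse square of the target difference, so error in that difference is greatly magnified. A pilot estimate that is high by chance leads to a full trial that is too small. One that is low by chance leads to a trial of impractical size, and one with the wrong sign gives no usable size at all. Section 2.2 says the study exists to supply parameters for designing the substantive trial, so a design parameter that is mostly noise matters to that purpose.

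This is a method the protocol states, not a detail it leaves to the statistical analysis plan. Estimating the difference and reporting it with its interval is no fault. Using it as the design effect is.

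**Working it through.** **The plan's own figure.** The Wald interval p ± 1.96·√(p(1−p)/n) with p = 0.30 and n = 60 gives 0.30 ± 1.96·0.0592 = 18.4% to 41.6%. This matches Table 1 (the text truncates the upper limit to 41%).

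**Size of the pilot.** 60 approached (3.5, 3.9) × 30% (3.5) = 18 randomised. At 1:1 that is 9 per arm, taking no loss to follow-up, which favours the plan. Across the interval for the rate, 11 to 25 are randomised.

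**Precision of the difference, in SD units.** SE = √(2/9) = 0.471. With 16 degrees of freedom, t = 2.120 and the half-width is 2.120 × 0.471 = 1.00 SD.

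| Recruitment rate | Per arm | 95% half-width (SD) |
|---|---|---|
| 18.4% | 5.5 | 1.36 |
| 30% | 9 | 1.00 |
| 41.6% | 12.5 | 0.83 |
| 70% | 21 | 0.62 |

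**Plug-in sizing.** The protocol gives no alpha, power or target effect. Assumed: two-sided 5%, 90% power, true effect 0.5 SD (0.3 and 0.8 also shown). The required n per arm is 2(1.960 + 1.282)²/d² = 21.0/d².

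- True d = 0.5 needs 21.0/0.25 = 84 per arm.
- Wrong sign: Φ(−0.5/0.471) = 14%.
- A trial sized on the estimate falls below 80% true power whenever the estimate exceeds the truth by the factor (1.960 + 1.282)/(1.960 + 0.842) = 1.157. That means an estimate above 0.579, only 0.079/0.471 = 0.17 SE too high.
- Treating the SD as known, the chance of this is Φ(−0.167) = 0.434. Among estimates with the right sign it is 0.434/0.856 = 51%.
- The same steps give 0.460/0.738 = 62% at a true 0.3 SD and 0.395/0.955 = 41% at 0.8 SD.

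A simulation of 400,000 pilots at 9 per arm, with the SD also estimated, agrees:

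| True effect (SD) | Wrong sign | True power below 80%, given right sign |
|---|---|---|
| 0.3 | 26% | 63% |
| 0.5 | 14% | 51% |
| 0.8 | 4.5% | 42% |

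At 0.5 SD, among right-sign pilots, the implied n per arm runs from about 15 to 900 (10th to 90th percentile), and 30% of the trials so sized have true power below 50%.

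**Would better recruitment help?** At 70% (21 per arm) and 0.5 SD, 42% of trials so sized are still below 80% power, and only 17% of the sizes lie within 25% of the correct one.

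**Comparator.** This run uses 80% power and total N, keeps every pilot and ignores the sign of the estimate. At a true 0.5 SD the correct total is 126. Sizing on the pilot difference gives 24 to 2852 (10th to 90th percentile), with 12% of pilots within 25% of 126. Fixing the difference in advance and taking only the SD from the pilot gives 74 to 186, with 52% within 25%.

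**The case against.** The strongest reply is that the sentence promises several candidate designs, not one sample size computed from one point estimate. The simulation therefore models a procedure that the protocol does not spell out. This stands in part: the percentages describe plug-in use and must be labelled so. It does not remove the point, because the pilot difference is the only source of effect that the section names, and a spread of designs built around it inherits its imprecision.

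A second reply is that the pilot's purpose (3.5) is the recruitment rate, and none of the four objectives in 3.2 is a sample size. That is correct and limits the severity.

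Three stronger readings are tempting, and the document supports none of them:

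- A reader might infer that the SD will be used as a bare point value. Section 4.2 says only that variability will be estimated and used. How its imprecision is handled may be left to the analysis plan.
- A reader might infer that costed full-trial designs are the study's main product. Sections 3.2 and 3.5 say otherwise, and 4.2 does not call the designs costed.
- A reader might infer that a low or wrong-sign estimate would stop a promising trial. No passage ties progression to the observed effect; feasibility rests on recruitment (3.5, 3.9).

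**Conclusion.** The concern holds in this form. Section 4.2 names the pilot's treatment differences as a power-analysis input, against the protocol's own statements about what the pilot can measure, and offers no alternative target effect. At 9 per arm the difference is known only to about ±1.0 SD. If the point estimate serves as the design effect, about half of the full trials so sized would have true power below 80% at a true effect of 0.5 SD (63% at 0.3 SD, 41 to 42% at 0.8 SD).

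These figures rest on the 30% planning rate, no dropout, two-sided 5%, 90% power, the listed true effects, and plug-in use. The conclusion does not depend on exactly 9 per arm, since 21 per arm gives much the same picture. It would be too strong to say that the recommended size will be largely random, because the section does not fix how the difference enters the range of designs.

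Severity: should-fix. The recruitment-rate estimate, the conduct of the pilot and its participants are unaffected.

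**What to change.** In section 4.2:

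1. Remove the estimated treatment differences as an input to the power analysis.
2. Size the candidate designs on a prespecified minimum important difference for NAHS (and for IHOT-33, the possible alternative primary outcome), or on a stated range of such differences.
3. Take only the SD, follow-up completeness and the recruitment rate from the pilot.
4. Report pilot differences descriptively, with confidence intervals.

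Optionally, show the designs over the uncertainty in the pilot SD. With 16 degrees of freedom its 95% interval is √(16/χ²) = 0.74 to 1.52 times the estimate, so required n could be 0.55 to 2.3 times the nominal figure.

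The cost is wording only; visits, data and conduct do not change. There are two downsides. The important difference has to be justified from outside the pilot, and the protocol supplies no value. The recommended size may also be larger: for example, sizing on the 80% upper limit of the SD (1.20 times the estimate) gives a median of 116 per arm against the 84 needed at 0.5 SD, about 38% more, in a setting that the protocol expects to be hard to recruit.

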5.1 Trial Supervision

Day-to-day management of the trial will be overseen by a Trial Management Group. A TSC -with an independent Chairman - and DMC will be set up.

The remit of the TSC is to:

- monitor and supervise the progress of the trial towards its interim and overall objectives
- review at regular intervals relevant information from other sources
- consider the recommendations of the DMC
- inform the funding body on the progress of the trial.

A DMC charter will be compiled detailing the members of the committee, their individual responsibilities and the overall responsibility of the DMC. The main roles of the DMC will be to review/approve the Statistical Analysis Plan (SAP), and to review trial progress, interim data and safety aspects of the study.

5.2 Quality control

We will institute a rigorous programme of quality control. The senior trial manager in conjunction with the trial coordinator will be responsible for ensuring adherence to the trial protocols at the trial sites. Quality assurance checks will be undertaken by Warwick CTU to ensure integrity of randomisation, study entry procedures and data collection. The Warwick CTU has a quality assurance manager who will monitor this trial by conducting regular (yearly or more if deemed necessary) inspections of the Trial Master File. Furthermore the processes of consent taking, randomisation, registration, provision of information and provision of treatment will be monitored. Written reports will be produced for the TSC, informing them if any corrective action is required.

[figure not shown]
5.3 Insurance and Indemnity Arrangements

Standard NHS cover for negligent harm is in place. There will be no cover for non-negligent harm.

